4.4. Study Procedures

Recruitment:

Convenience sampling strategy will be used to recruit participants for this study. Bilingual recruitment flyers will be distributed via JFK Family Medicine Center, Plainfield Health Connections, the Diabetes Center at JFK, a community-based family practice located in Plainfield, places of worship, and other community centers in the Middle Atlantic Region. Eligible participants will be invited to enroll in the study. Upon agreement to participate in this study, informed consent will be obtained electronically using REDCap or via paper-and-pencil format. Approximately 30 minutes will be given for questions and answers during the consent process. Efforts will be made to ensure participants know in advance that attending the educational program requires participation in the study.

Procedures:

1. The PI, a board-certified adult nurse practitioner with more than 10 years of experience in health education and caring for persons with T2DM, will be implementing the culturally tailored diabetes self-management education (C-DSME) intervention in this study, accompanied by a certified Spanish medical interpreter.
2. The intervention will be delivered to all participants in group sessions for five (5) consecutive weeks using a hybrid format (first and last sessions will be in person) in a private classroom at the HMM JFKUMC School of Nursing in Plainfield, on the same campus as Plainfield Health Connections. A Google Meet link will be shared each week as part of the class reminder texts via secure Twilio messaging using REDCap.
3. Each session will last approximately two (2) hours.
4. An electronic (via REDCap) or paper-and-pencil copy of the Spanish version (certified and validated) of the Summary of Diabetes Self-Care Activities survey

(Toobert et al., 2000; Vincent et al., 2008) will be completed by each participant during Week 1 ((pre-intervention) and again in Week 5 (post-intervention) for comparison.

5. Assistance with survey completion will be available from the PI and medical interpreter as needed.
6. This C-DSME intervention will be modeled after the ADCES7 Framework, derived from national standards and consistent with current, evidence-based clinical practice guidelines for T2DM education in adults (ADA, 2022; ADCES, 2021; Powers et al., 2021). The main focus will be on three of the seven ADCES7 self-care behaviors, namely, (a) Healthy Eating, (b) Staying Active, and (c) Medication Use (ADCES, 2021).
7. Pertinent bilingual educational materials downloaded from the ADA and ADCES websites will be distributed to participants during weekly sessions. The C-DSME intervention will cover the following components and will be structured as follows:

Week	Educational Content/Intervention	Duration (in minutes)	Survey Administration
Week 1	Brief overview of T2DM; healthy coping; healthy eating - cultural beliefs about food.	60 minutes	60 minutes
Week 2	More in-depth discussion on healthy eating, including MyPlate method of meal planning for persons with T2DM; incorporation of fruits and vegetables in daily meals; consumption of whole grains, lean meats and other proteins; healthy fats and oils; healthy snacks and beverages.	120 minutes	N/A
Week 3:	Discussion will focus on physical activity and exercise; participants' beliefs and values regarding exercise will be explored; benefits of exercise will be discussed, and each participant will be encouraged to commit to a weekly exercise regimen in accordance with ADA and American Heart Association (AHA) guidelines.	120 minutes	N/A

Week	Educational Content/Intervention	Duration (in minutes)	Survey Administration
Week 4:	Participants' beliefs and values regarding medication use will be explored. Topics to be covered will include rationale for medication use; indications; dosage; frequency; adherence; herbs and supplement use; among others.	120 minutes	N/A
Week 5:	This interactive class will include discussions on self-monitoring, reducing risks, and problem solving. Participants will be given a chance to ask more questions, provide feedback, and interact with each other. They will also be invited to share what they have learned and how it can be applied to enhance their daily self-care practices.	60 minutes	60 minutes

Compensation:

Each participant will receive a \$25 Visa card to offset transportation cost after participation in all 5 sessions.

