5.6. Follow-up and end-of study (if applicable)

5.7. Statistical Method

5.7.1. Sample size calculation and justification

A priori power analysis was completed to guide sample size determination (Cohen, 1992). This was done to control for the potential threat to statistical conclusion validity that can occur due to low statistical power, often associated with inadequate sample size selection (Gray et al., 2017).

Based on published SDSCA data for diet and a calculated effect size of 0.41 (doi:10.1177/0145721712443292), an alpha of 0.05 and power of 0.80 for a paired two-sided test, a sample size of 49 is adequate. Assuming a 50% incompleteness rate, a sample size of 98 would be able to detect a pre- and post-survey difference at 80% power ([R version 4.3.3; `pwr.t.test`]; Cohen, 1992; Choi & Rush, 2012; Kang, 2021; Plichta & Kelvin, 2013).

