5.7.2. Statistical Analysis Plan

Efficacy Analyses

All continuous variables will be summarized using the following descriptive statistics: n (non-missing sample size), mean, standard deviation, median, maximum and minimum. Discrete data will be summarized using n (non-missing sample size), median, minimum,

maximum, and interquartile range or semi-interquartile range. The frequency and percentages (based on the non-missing sample size) of observed levels will be reported for all categorical measures. All summary tables will be annotated with the total population size relevant to that table/timepoint, including any missing observations. Note that sample sizes for individual variables may be different than for the complete case analyses as data in the summary tables may/ may not be present as compared to the complete case dataset.

Primary Efficacy Analysis

Primary outcome(s):

- 1) To determine the efficacy of DSME in the adult Hispanic male population on healthy eating.
 - Hypothesis: N/A
 - Variable: Eating questions (numeric: number of days)
 - Measurement: average number of days
 - Summary data: Mean and SD or median and min/max/SIQR will be calculated for numeric data, as appropriate. Results will be presented in a table, stratified by time.
 - Preliminary Model(s): Data will be modeled using linear regression, generating betas and 95% confidence intervals (PMID: 34325755). Variables included in the model will be the average number of days regressed on time (pre- and post-educational intervention). Results will be presented in a table. Models will be run as two-sided with significance levels set at 0.05. Assumptions for the model will be tested using visualizations, as appropriate.
- 2) To determine the efficacy of DSME in the adult Hispanic male population on staying active.
 - Hypothesis: N/A
 - Variable: Activity questions (numeric: number of days)
 - Measurement: average number of days
 - Summary data: Mean and SD or median and min/max/SIQR will be calculated for numeric data, as appropriate. Results will be presented in a table, stratified by time.

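### Participants are taught in group classes, but the sample size and model treat them as independent; once the pre-post pairing is modelled, intervals that ignore class may be too narrow, and the 80% power assumes no within-class correlation of change.

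*Combined protocol and SAP*

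**What the plan says.** Section 4.4 describes the delivery: "The intervention will be delivered to all participants in group sessions for five (5) consecutive weeks using a hybrid format". Sections 4.4 and 5.3 describe interactive teaching, with discussion of participants' beliefs and values; for Week 5, section 4.4 adds: "Participants will be given a chance to ask more questions, provide feedback, and interact with each other". One person, the principal investigator, teaches everyone, with an interpreter, in one classroom or by video link. The study lasts 12-18 months (4.1.1). The number and size of classes are not stated, and class is not among the data items listed in 5.5 and 6.4.

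The sample size in 5.7.1 is an individual-level calculation: "Based on published SDSCA data for diet and a calculated effect size of 0.41", with "an alpha of 0.05 and power of 0.80 for a paired two-sided test, a sample size of 49 is adequate". It then doubles the number: "Assuming a 50% incompleteness rate, a sample size of 98 would be able to detect a pre- and post-survey difference at 80% power". It has no design effect, class size or within-class correlation.

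The model in 5.7.2 is the same for all three outcomes: "Data will be modeled using linear regression, generating betas and 95% confidence intervals". For diet and exercise, "Variables included in the model will be the average number of days regressed on time (pre- and post-educational intervention"); for medication the response is the number of days. There is no class term, no cluster-robust variance and no participant term.

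**The concern.** Men who take the same class share a group, a season and a run of sessions. If their changes are alike for those reasons, 49 completers carry less information about the mean change than 49 independent men. A paired analysis that ignores this understates the standard error, and the power in 5.7.1 is then too high. All three primary outcomes are affected, because all three use the same model.

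The correlation that matters is that of the pre-post change. Stable differences between classes at baseline cancel in a paired analysis.

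**Working it through.** **Inputs from the plan (5.7.1).** Effect size 0.41 (diet only), two-sided alpha 0.05, power 0.80, paired test, 49 completers, 50% incompleteness, 98 enrolled.

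**Inputs assumed, because the documents give none.** Completers per class m = 5 or 10; ICC of the pre-post change 0.01, 0.05 or 0.10; pre-post correlation rho from 0 to 0.7.

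**1. The plan's own figure.** Paired t-test, noncentral t distribution: power is 79.4% at n = 48 and 80.3% at n = 49, so 49 is the smallest adequate number. 49/(1 - 0.5) = 98. Both figures reproduce.

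**2. Power when changes correlate within class.** Design effect DE = 1 + (m - 1) x ICC; effective n = 49/DE; power from the noncentral t with effective n - 1 degrees of freedom.

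| m | ICC | DE | effective n | power |
|---|---|---|---|---|
| 5 | 0.01 | 1.04 | 47.1 | 79% |
| 5 | 0.05 | 1.20 | 40.8 | 73% |
| 5 | 0.10 | 1.40 | 35.0 | 65% |
| 10 | 0.01 | 1.09 | 45.0 | 77% |
| 10 | 0.05 | 1.45 | 33.8 | 64% |
| 10 | 0.10 | 1.90 | 25.8 | 52% |

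**3. Degrees of freedom with few classes.** The table does not include a small-sample correction. With 10 per class, 49 completers form about five classes, so a class-based analysis has about 4 degrees of freedom. The critical value rises from 2.01 to 2.78 (2.78/2.01 = 1.38). Power is then about 58% at ICC 0 and about 44% at ICC 0.05.

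**4. Interval from a paired analysis that ignores class.** It should be wider by the square root of DE. For m = 10 that is 1.04, 1.20 and 1.38 times at ICC 0.01, 0.05 and 0.10. The true two-sided error, 2 x (1 - Phi(1.96/sqrt(DE))), is about 6%, 10% and 15% instead of 5%.

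**5. Interval from the model as written.** Regressing score on time alone gives a variance of 2 x sigma^2/n for the time effect. The true variance of the mean change is 2 x sigma^2 x (1 - rho) x DE/n, taking equal pre and post variances. The reported standard error divided by the true one is therefore 1/sqrt((1 - rho) x DE). With m = 10 and ICC 0.05 (DE = 1.45):

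- rho = 0: 0.83
- rho = 0.3: 0.99
- rho = 0.5: 1.17
- rho = 0.7: 1.52

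The written interval is too narrow only if DE exceeds 1/(1 - rho). At rho = 0.5 that means DE above 2, which is an ICC above 1/9 = 0.11 with 10 per class, or above 1/4 = 0.25 with 5 per class.

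**6. Slack from lower attrition.** At m = 10, the completers needed are 49 x 1.18 = 58 at ICC 0.02 (58/98 = 59% of those enrolled) and 49 x 1.45, rounded up to 72, at ICC 0.05 (72/98 = 73%), before any small-sample correction.

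**The case against.** A reader might infer that the planned intervals will be too narrow for all three outcomes. The documents do not support that. The model in 5.7.2 also drops the pairing, and this widens the interval whenever pre and post scores correlate positively. Over much of the plausible range it outweighs the clustering (step 5). The narrow-interval claim belongs to a paired analysis that ignores class. That is still the right reference, because 5.7.1 assumes a paired test, and repairing the pairing alone would remove the offset.

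A reader might also take one row of the table as the actual loss. It is not: class number, class size and ICC are all assumed, and even the existence of several classes is inferred.

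Some features of the plan should hold the correlation down. One instructor teaches every class, section 5.3 commits to uniform delivery, only the first and last sessions are fixed as in person, and in virtual sessions cameras may be off. The Week 5 interaction comes just before a survey about the previous seven days, so it can hardly have influenced those answers. All this argues for a smaller ICC, but not for zero: discussion also takes place in the earlier weeks, and season and group are still shared.

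Finally, if fewer than half drop out, the extra completers recover power. That stands, but extra completers do not correct an interval that ignores class.

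**Conclusion.** The point holds in conditional form. The delivery is in groups, and nothing in the sample size or the analysis allows for it. The 80% at 49 completers is right only if changes are uncorrelated within class. Under the assumed class sizes and ICCs it falls to between 79% and 52%, and lower still once the degrees of freedom reflect a handful of classes. A properly paired interval that ignores class would be too narrow if that correlation is positive. For the unpaired model as written, the net error may go either way.

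This is worth correcting but is not decisive: its size cannot be fixed from the documents, and the missing pairing has to be repaired with it. A class term would not separate the instructor from the programme, since one instructor teaches all classes.

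**What to change.** - **Data collection.** Record a class ID for every participant from the first class, and state the planned number and size of classes.
- **Section 5.7.2.** Analyse the paired change, or use a model with a participant effect. Beside it, report an analysis that allows for class: a random class effect on change, or a cluster-robust variance, with a small-sample correction. If there are too few classes to estimate this, report class-specific changes and state that the interval is conditional on these classes. Do not present a fixed class effect as a correction, because it takes between-class variation out of the standard error. If only one class is run, state the limitation.
- **Section 5.7.1.** State that 80% at 49 completers assumes zero within-class correlation of change. Give the range in step 2 with class size and ICC labelled as assumptions. Add that it omits the small-sample correction (about 58% at ICC 0 and 44% at ICC 0.05 with about five classes of 10), and that completers beyond 49 would recover some power.

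The cost is one recorded variable and some wording; no extra participants are needed. The downside is wider intervals, possibly much wider with few classes, and a less favourable power statement. Class ID should be captured now, since 5.5 and 6.5.2 provide for paper forms to be destroyed after transfer and membership may be hard to reconstruct later.

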3.4. Primary Outcome Variable

Title: Diabetes Self-Management (DSM) Behaviors

Description: DSM will be measured by self-reported data on diet, exercise, and medication adherence, utilizing scoring derived from the Spanish version of the Summary of Diabetes Self-Care Assessment (SDSCA-Sp) scale. SDSCA-Sp core items measure participants' DSM activities during the past seven days. In case of sickness during that period, participants are asked to respond based on the last seven days they were not sick.

Scoring: Scores will be calculated separately for each subscale of the instrument. Number of days per week an activity is performed, on a 0–7 scale, is recorded, with higher numbers corresponding to higher levels of self-care activity performance (Toobert et al., 2000; Vincent et al., 2008).

Primary Outcome Measure 1**Title:** Healthy Eating**Description:** Healthy eating behaviors will be measured by self-reported data on diet adherence utilizing scoring derived from the SDSCA-Sp scale.**Scoring:** Items 1–5 relate to dietary behaviors, for example, “how many of the last seven days have you followed a healthful eating plan?” Diet will be scored using the mean number of days for items 1-5, using a reverse score for item 4 (Toobert et al., 2000; Vincent et al., 2008).**Primary Outcome Measure 2****Title:** Staying Active**Description:** Physical activity behaviors will be measured by self-reported data on exercise adherence utilizing scoring derived from the SDSCA-Sp scale.**Scoring:** Items 6–7 pertain to exercise activity, for example, “on how many of the last seven days did you participate in at least 30 minutes of physical activity?” Exercise will be scored using the mean number of days for items 6 and 7.**Primary Outcome Measure 3****Title:** Medication Use**Description:** Medication use behaviors will be measured by self-reported data on medication adherence utilizing scoring derived from the SDSCA-Sp scale.**Scoring:** Medication use will be scored using total number of days for item 12.**Timeframe:** Self-reported data will be collected at Week 1 (baseline) and Week 5 (following implementation of educational sessions). The timeframe of instrument completion is 45-60 minutes.**3.5. Secondary Objective(s)**

N/A

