5.3. Study Intervention (including schedule of events and study visits)

The PI, a board-certified adult nurse practitioner with more than 10 years of experience in health education and providing care to persons with T2DM, will be implementing the C-DSME intervention in this study, accompanied by a certified Spanish medical interpreter. This educational intervention will be delivered in group sessions for five (5) consecutive weeks using a hybrid format (via Google Meet) and at the HMH JFKUMC School of Nursing classroom across from the Plainfield Health Connections office with each session lasting approximately two (2) hours (for a total of 10 hours over the five week period).

The Spanish version of the Summary of Diabetes Self-Care Activities survey (Appendix B) will be completed by each participant electronically (via REDCap) or via paper and pencil (with assistance from the PI and interpreter as needed) at the beginning of Week 1 (pre-intervention) and again at the end of Week 5 (post-intervention) for comparison.

This C-DSME intervention will be modeled after the ADCES7 Framework, derived from national standards and consistent with current, evidence-based clinical practice guidelines for T2DM education in adults (ADA, 2022; ADCES, 2021; Powers et al., 2021). The main focus will be on three of the seven ADCES7 self-care behaviors, namely, (a) Healthy Eating, (b) Staying Active, and (c) Medication Use (ADCES, 2021).

Pertinent bilingual educational materials downloaded from the ADA and ADCES websites will be distributed to participants during weekly sessions. The C-DSME intervention will cover the following components and will be structured as follows:

- **Weeks 1–2:** A brief overview of T2DM will be provided, followed by discussions on healthy coping, cultural beliefs about food; healthy eating, including MyPlate method of meal planning for persons with T2DM; incorporation of fruits and vegetables in daily meals; consumption of whole grains, lean meats and plant-based proteins; healthy fats and oils; healthy snacks and beverages.
 - Healthy snacks and water will be provided during classes.
 - Participants will receive culturally friendly recipes to try at home.
 - A compilation of local grocery stores carrying affordable, healthy foods will be distributed.
 - Sessions will be interactive and engaging, and will involve the use of visual aids, pictographs, and teaching aids to enhance learning.

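### The post-survey closes the last class and may be completed with the teaching investigator's help, which is likely to shift self-reports upward in a study with no control group

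*Combined protocol and SAP*

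**What the plan says.** - **Who teaches and who helps.** Section 4.4 says that the PI "will be implementing the culturally tailored diabetes self-management education (C-DSME) intervention in this study", accompanied by a Spanish interpreter. The same section says: "Assistance with survey completion will be available from the PI and medical interpreter as needed". Section 5.3 repeats the offer for both surveys.
- **When the surveys are taken.** Section 5.3 places them "at the beginning of Week 1 (pre-intervention) and again at the end of Week 5 (post-intervention) for comparison". Section 3.4 says: "Self-reported data will be collected at Week 1 (baseline) and Week 5 (following implementation of educational sessions".
- **What happens in Week 5.** The Section 4.4 table gives 60 minutes to class and 60 minutes to the survey. Of the participants in that class it says: "They will also be invited to share what they have learned and how it can be applied to enhance their daily self-care practices". On the hybrid format, the section notes that the "first and last sessions will be in person".
- **What is measured.** Section 3.4 defines all three primary outcomes (diet, exercise, medication) by self-report, with core items covering "DSM activities during the past seven days". There are no secondary outcomes and no objective measure.
- **Design and stated safeguards.** Section 4.1 specifies one group with no control. The validity discussions in Sections 5.3 and 6.5.8 rely on participants acting as their own control; 5.3 adds uniform delivery. Neither mentions social desirability or who administers the survey. Section 4.5.1 provides for coded surveys and skippable questions. Under Section 6.3 the list linking names to study IDs is accessible only to the PI.

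**The concern.** A pre-post comparison in one group is interpretable only if the conditions of reporting are the same at both times. Here they differ in two ways, and both point towards apparent benefit. First, the pre-survey comes before any teaching, whereas the post-survey comes at the end of a session in which participants talk about applying what they were taught. Second, the person who may help with the form is a new acquaintance in the course at Week 1, but by Week 5 has taught the desired behaviours. A participant whose behaviour has not changed has more reason to report a favourable number of days at Week 5 than at Week 1. Acting as one's own control does not remove a change in reporting conditions. With no comparison group and no objective measure, nothing in the analysis could separate such a shift from a real effect on any of the three primary outcomes.

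**Working it through.** **1. Reproduce the plan's own figure.** Inputs from Section 5.7.1: effect size 0.41, two-sided alpha 0.05, power 0.80, paired test, 50% incompleteness.

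Power = P(|T| > t₀.₉₇₅,ₙ₋₁), where T is noncentral t with n−1 degrees of freedom and noncentrality d√n.

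- n = 48: power 0.794.
- n = 49: noncentrality 0.41 × 7 = 2.87, power 0.803.
- Enrolment: 49 / (1 − 0.50) = 98.

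The stated 49 and 98 both reproduce.

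**2. Chance of significance from reporting alone.** Set the true change in behaviour to zero and let reports rise by b SDs of the paired difference. The same formula applies with b in place of d. The documents give no size for b, so every value below is an assumption. The second column is the planned number of completers; the third would apply if nobody were lost.

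| Assumed shift b | P(p<0.05), 49 pairs | P(p<0.05), 98 pairs |
|---|---|---|
| 0 | 5% | 5% |
| 0.1 | 10.5% | 16.5% |
| 0.2 | 27.9% | 50.0% |
| 0.3 | 53.9% | 83.7% |

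For example, b = 0.2 with 49 pairs has noncentrality 0.2 × 7 = 1.4.

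The smallest observed mean change that reaches p<0.05 is t₀.₉₇₅,ₙ₋₁/√n: 2.011/7 = 0.29 SD with 49 pairs and 0.20 SD with 98. Both are below the planned 0.41. Better retention makes a false positive from this source more likely.

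These rates are per outcome and use the paired test of Section 5.7.1. Section 5.7.2 describes a linear regression on time; a version that ignored the pairing would give different rates.

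**3. Does the late slot buy anything?** Sessions run in five consecutive weeks. Assuming seven-day spacing, session 1 is day 0, session 4 is day 21 and session 5 is day 28. A seven-day recall at session 5 covers days 21 to 28. If a participant was ill, the instructions in Section 3.4 move the window earlier, not later. Either way it ends no later than session 5, so the Week 5 class cannot have changed the behaviour being reported. It can change only how that behaviour is reported. Completing the survey before the class therefore loses no measurable effect.

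**The case against.** Several objections stand.

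- **Help is symmetric.** The same helpers are offered at both surveys, as needed, and both sessions are in person. Assistance alone need not bias the change score. A reader might infer that the investigator helps only at follow-up; the documents do not say that.
- **The order within Week 5 is partly inferred.** Section 5.3 says end of Week 5 and the Section 4.4 table puts class and survey in one session, but no minute-by-minute order is given and the sharing discussion is one of several activities. That the survey comes immediately after that discussion is not established.
- **Survey mode.** Paper or REDCap is allowed, with no rule keeping one mode per participant. A reader might infer a further bias towards benefit. Nothing in the documents gives a direction for a mode effect, and Section 5.5 describes both formats as acceptable.
- **The illustration is generic.** It applies to any reporting shift in a one-group study. It does not show how much is due to the helper or the order, nor how much a change would remove.
- **The interpreter is not neutral.** The interpreter attends the classes and is coached on the study's purpose and design (Sections 4.2.3, 4.4, 4.5.1).
- **The missing control group is already acknowledged.** Sections 5.3 and 6.5.8 name it as a threat to internal validity, though not this mechanism.

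It may also be objected that surveying before class 5 departs from the five-week wording of the hypotheses in Section 3.2. By the recall argument above, the present timing measures the same days of behaviour, so that tension exists already.

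These points limit the strength of the claim. They do not justify keeping an order that gains nothing, or having the teacher help with the outcome measure.

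**Conclusion.** The point holds as a likely and partly avoidable upward reporting bias on all three primary outcomes. It rests on the survey order, the teacher's role as possible helper, self-report as the only measure, and the absence of a control group, all of which are in the documents. The direction is an expectation and the size is unknown. The 28% and 54% figures (49 pairs, shifts of 0.2 and 0.3 SD) show how small a shift would matter if it occurred; they do not estimate what will occur. A reader might infer that the plan demonstrably inflates improvement, or that a positive result would be artefact; the documents support neither. This is an improvement that should be made, and it leaves the sample size calculation untouched.

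**What to change.** Amend Sections 4.4 and 5.3, and align 3.4:

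1. The investigator does not assist with or observe survey completion at either time point. When help is needed, the interpreter, already present, reads items verbatim without comment.
2. The Week 5 survey is completed before that class begins, mirroring Week 1. Describe the outcome as behaviour in the seven days before session 5, and change the Section 3.4 wording that places the survey after the sessions.
3. State the remaining reporting bias as a limitation, including that the interpreter is not fully independent.

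Keeping each participant on one survey mode is a sensible minor consistency measure, not a correction of a demonstrated bias.

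Moving the survey to a REDCap link a week or more after session 5 is not recommended. It gives up in-person collection when Section 5.7.1 already assumes 50% incompleteness, and Section 4.3 excludes withdrawn participants who lack a post-survey.

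Cost: protocol wording, a swap of two 60-minute blocks within the existing two-hour session, and IRB approval of the modification under Section 6.2. No extra staff are needed, but the interpreter takes all requests for help. The bias is reduced, not removed: four sessions with the same teacher still precede the survey.
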